8.1.5 Statistical Analyses of Efficacy

The efficacy analysis will be conducted in the ITT Population, and Per-protocol Population if defined, in each Period. Visit windows and the data handling conventions for summarizing efficacy results will be defined in the Statistical Analysis Plan. Missing data will be imputed using the following methods for the efficacy analyses in the ITT Populations:

- Non-Responder Imputation (NRI): the NRI analysis will categorize any subject who has missing value at a specific visit as non-responder for that visit. In NRI analysis, subjects who prematurely discontinue study drug will be considered non-responders on or after discontinuation date. NRI will be the primary approach for binary endpoints.
- Last Observation Carried Forward (LOCF): The LOCF analyses will use the completed evaluation from the previous visit to impute missing data at later visits. Baseline value will not be carried forward. LOCF will be the primary approach in the analysis of continuous variable, and the secondary approach in the analysis of categorical variables.

- As-observed (OC): The OC analysis will not impute values for missing evaluations, and thus a subject who did not have an evaluation on a scheduled visit will be excluded from the as observed analysis for that visit. As-observed analysis will be the secondary approach in the analysis of continuous variables.
- Multiple Imputation (MI): The MI analysis imputes missing data multiple times under appropriate random variation and thus generates multiple imputed "pseudo-complete" datasets. Results will be aggregated across the multiple imputed datasets, overcoming drawbacks of the single imputation methods. MI will be performed for the primary efficacy variable and the proportion of subjects achieving IGA of "clear" or "almost clear" and EASI 75 at Week 16.

Efficacy parameters for the subjects who are rescued with 30 mg ABT-494 or topical corticosteroids in Period 2, and subjects who discontinued study drug due to EASI score worsening during Period 1 will be imputed from the point of rescue using non-responder imputation for categorical variables or LOCF for the continuous variables.

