#### **4.2 Design Diagram**

This is an 88-week Phase 2b, randomized, double-blind, parallel-group, placebo-controlled multicenter study of safety and efficacy of upadacitinib in adult subjects with moderate to severe AD.

The duration of the study will be up to 88 weeks and will include a 35-day maximum screening period, a 16-week double-blind treatment period (Period 1) and a 72-week double-blind treatment period (Period 2). In addition, a 30-day follow-up visit (or phone

---

call if a visit is not possible) should occur to determine the status of any ongoing AEs or serious adverse events (SAEs), or the occurrence of any new AEs/SAEs.

**Period 1:** A 16-week double-blind, placebo-controlled treatment period during which subjects will be randomized in a 1:1:1:1 ratio to one of four treatment groups:

- Group 1: upadacitinib 7.5 mg once daily (QD) for 16 weeks
- Group 2: upadacitinib 15 mg QD for 16 weeks
- Group 3: upadacitinib 30 mg QD for 16 weeks
- Group 4: Matching Placebo for 16 weeks

Randomization will be stratified by geographic region (US/PR/Canada, EU/AUS, and Japan). Enrollment in Japan will be capped at 10% of subjects (4 subjects per group).

In Period 1, discontinuation from study drug will be mandatory for any subject with an Eczema Area and Severity Index (EASI) score worsening of 25% or more compared with their baseline EASI score at any 2 consecutive scheduled study visits from Week 4 to Week 12.

**Period 2:** a 72-week double-blind, placebo controlled treatment period during which subjects who complete Period 1 will be re-randomized at Week 16 within their original treatment group assignments to either upadacitinib or placebo into a 72-week double-blind, placebo controlled treatment period in a 1:1 ratio as shown in [Figure 1](#) (study design). Randomization will be stratified by geographic region and the improvement of EASI score by at least 75% (EASI 75 response) at Week 16. At the Week 16 visit, all subjects will be re-randomized as follows into Period 2:

- Group 1 in Period 1: upadacitinib 7.5 mg QD or matching placebo for 72 weeks
  - Group 2 in Period 1: upadacitinib 15 mg QD or matching placebo for 72 weeks
  - Group 3 in Period 1: upadacitinib 30 mg QD or matching placebo for 72 weeks
-

- Group 4 in Period 1: upadacitinib 30 mg QD or matching placebo for 72 weeks

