Starting at the Week 20 visit (4 weeks after re-randomization into Period 2), rescue therapy with upadacitinib 30 mg QD will be provided to subjects who have a first instance of an EASI score improvement of less than 50% (i.e., < EASI 50 response), when compared against the Baseline. These subjects will continue on upadacitinib 30 mg QD for the remainder of the study.

[figure not shown]
During Period 2, concomitant class III – IV, medium potency topical corticosteroid treatment will be permitted at the Week 24 visit and thereafter in subjects after a second instance of < EASI 50 response in any two Period 2 study visits beginning from Week 20 (see Protocol Section 5.2.3.4 for permitted treatments). For subjects who receive topical corticosteroid rescue therapy, a visit will be required 4 weeks after receiving the rescue therapy. Discontinuation from study drug will be mandatory for subjects with < EASI 50 response compared with their baseline EASI score 4 weeks following rescue with topical corticosteroids or at any visit thereafter.

In order to minimize missing data for efficacy and safety assessments, subjects who prematurely discontinue study drug should continue to be followed for all regularly scheduled visits, unless they have decided to discontinue the study participation entirely (withdrawal of informed consent).

A schematic of the overall study design is shown in [Figure 1](#).

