**Table 2. Analysis Windows for EASI, SCORAD, IGA, BSA, PGIS, Laboratory Parameters, and Vital Sign Variables (Period 1)**

Scheduled Week	Nominal Day	P1 Rx Day Interval
Baseline	1	$\leq 1$
Week 2	15	2 – 22
Week 4	29	23 – 43
Week 8	57	44 – 71
Week 12	85	72 – 99
Week 16	113	100 – 126 a

a. Minimum of the upper bound and the day of the first dose in Period 2.

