### 10.1.5 Missing Data Imputation

Missing data will be imputed using the following methods for the efficacy analyses:

- Non-Responder Imputation (NRI): the NRI analysis will categorize any subject who does not have evaluation during a specific visit window as a non-responder for that visit. The exception is when the subject is a responder both before and after a specific visit window, in which case the subject will be categorized as a responder for the visit. Only observations within the same analysis period will be used. The NRI will be the primary approach in the analyses of categorical variables.

- Last Observation Carried Forward (LOCF): The LOCF analyses will carry forward the most recent previous non-missing value (last completed non-missing value, for composite endpoint) to impute missing data at later visits in the same period. Baseline efficacy evaluations will not be carried forward. LOCF will be the primary approach in the analyses of continuous variables, and the secondary approach in the analysis of categorical variables.
- As-Observed Cases (OC): The as-observed analysis will not impute values for missing evaluations, and thus a subject who does not have an evaluation on a scheduled visit will be excluded from the as-observed analysis for that visit. As-observed analysis will be the secondary approach in the analysis of continuous variables.
- Multiple Imputation (MI): The MI approach will be used for sensitivity analyses on the Week 16 endpoints of EASI percent change from Baseline, EASI 75, and the Investigator Global Assessment (IGA) response of 0 (clear) or 1 (almost clear). If MI is not applicable due to the nature of the data (e.g., MCMC algorithm does not converge), logistic regression or mixed effect model repeat measurement (MMRM) methods will be applied as the sensitivity approach, whichever applicable.

The Multiple Imputation analysis will be carried out in three steps.

- Imputation of missing data. The imputation will be generated for each efficacy endpoint measurement. The variables to be included in the imputation model are: Baseline EASI (or IGA), treatment group, and measurements at each visit up to the end of the analysis period. For each endpoint, 20 'complete' datasets will be generated using SAS PROC MI. The imputed post-baseline measurements will be rounded to the same precision as the observed data before the determination of responder status (e.g., EASI 75 and EASI percentage change from Baseline).

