  - Analysis of imputed data sets. Using the corresponding statistical methods for the categorical and continuous endpoints, the imputed endpoints from Step 2 will be analyzed using each of the 20 datasets.
-

- Synthesis of imputation and analysis results. SAS PROC MIANALYZE will be used to generate the final inferences of the risk difference between treatment groups.

Of note, subjects who take rescue upadacitinib 30 mg or take rescue topical treatment in Period 2 will have their efficacy assessments taken from the date after the first dose of rescue excluded from the analyses, as the result, the subjects will be considered as non-responders in the NRI approach, and have their last observations on or prior to the date of rescue carried forward, and be removed from the OC approach.

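### SAP 10.1.5 does not carry over two protocol 8.1.5 rules for data after study drug is stopped (Period 1 EASI-worsening stops, and non-response after any stop under NRI), and SAP 12.1 does not declare the change

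*SAP*

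**What the plan says.** **Protocol 8.1.5** contains two rules that apply even when an evaluation exists.

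- Rule (a): "subjects who discontinued study drug due to EASI score worsening during Period 1 will be imputed from the point of rescue", by NRI for categorical variables and LOCF for continuous ones. The same sentence covers subjects rescued in Period 2.
- Rule (b), within the NRI definition: "subjects who prematurely discontinue study drug will be considered non-responders on or after discontinuation date". It is not limited to one period or to one reason for stopping.

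**SAP 10.1.5** defines the methods afresh. For NRI, "the NRI analysis will categorize any subject who does not have evaluation during a specific visit window as a non-responder for that visit". LOCF fills missing data at later visits from the latest non-missing value in the same period. The only removal of observed data is the closing note on rescue: "subjects who take rescue upadacitinib 30 mg or take rescue topical treatment in Period 2 will have their efficacy assessments" excluded after the first rescue dose. Neither rule (a) nor rule (b) appears.

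**SAP 4.2** repeats the Period 1 stop: "discontinuation from study drug will be mandatory for any subject with an Eczema Area and Severity Index (EASI) score worsening" of at least 25% over Baseline at two consecutive visits between Weeks 4 and 12. It also says that "subjects who prematurely discontinue study drug should continue to be followed for all regularly scheduled visits", unless consent is withdrawn. Protocol 5.4.1 and 6.1.7 describe these subjects as being on standard of care.

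**SAP 12.1** lists four changes from the protocol: baseline tests, the quadratic model, DLQI, and the added pruritus NRS endpoint. None concerns imputation.

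**The concern.** The two documents give different Week 16 values for the same subject. Under the SAP text, a subject who stops for worsening and then improves on standard of care contributes that improvement to the randomized arm's primary endpoint. Under the protocol, the same subject contributes the value carried from the stop. Likewise, a subject who stops for any reason in Period 1 and is a responder off drug at Week 16 counts as a responder under SAP NRI and as a non-responder under protocol NRI.

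If worsening stops are more frequent on placebo and EASI then improves on standard of care, the SAP handling shrinks the difference from placebo. If stop rates and off-drug values are equal across arms, the difference does not change. The direction and size therefore depend on data not yet seen, which is why the rule has to be fixed in advance.

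**Working it through.** **1. Does other SAP text fill the gap?** No.
- The Week 16 EASI window in SAP Table 2 is days 100 to 126. Its only limit is "Minimum of the upper bound and the day of the first dose in Period 2", so there is no cut-off at last dose.
- SAP 10.3 adds only that LOCF is used.
- Where the SAP wants a last-dose cut-off it says so: SAP 11.3 drops laboratory values taken more than 30 days after the last dose.

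**2. Does document timing explain it?** No. SAP 3.0 implements the protocol of 07 June 2017. Protocol Appendix Q shows that the later amendment changed only 6.1.1.3 and 8.1.6.2.1.

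**3. Which analyses are affected?**

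| Situation | Protocol 8.1.5 | SAP 10.1.5 |
|---|---|---|
| Worsening stop, Week 16 EASI observed, primary endpoint | LOCF from the stop | Observed off-drug value |
| Worsening stop at Week 8, off-drug Week 12 value, Week 16 missing, primary endpoint | LOCF from the stop | Off-drug Week 12 value carried forward |
| Other stop (for example an AE), continuous endpoint | Observed value | Observed value (no discrepancy) |
| Any Period 1 stop, Week 16 observed, NRI comparison | Non-responder | Responder if the off-drug value qualifies |
| No Week 16 value after a stop, NRI | Non-responder | Non-responder |
| Period 2 stop after rescue, NRI | Non-responder | Non-responder |
| Period 2 stop without rescue, NRI | Non-responder | Responder if the off-drug value qualifies |

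The binary MCP-Mod analyses use LOCF (SAP 10.1.4), so rule (b) does not reach them. Period 2 summaries are descriptive (SAP 10.1).

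**4. Do the alternative analyses show the effect?** No. MI imputes only missing data, and for OC "The as-observed analysis will not impute values for missing evaluations". Both keep the off-drug values.

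**5. Scale.** Inputs from SAP 4.3: 40 per arm, SD 40, planned differences from placebo of 70 − 35 = 35 (30 mg) and 60 − 35 = 25 (15 mg).
- Standard error of a pairwise difference: 40 × √(2/40) = 8.94. The noncentral t with 78 df gives power of 97.2% and 78.8%, against the stated 97% and 78%. The plan's figures reproduce.
- Binary, Period 1: 1/40 = 2.5 percentage points per reclassified subject.
- Binary, Period 2: 40/2 = 20 per arm if all are re-randomized, so 1/20 = 5 points (more if arms are smaller).
- Primary: assume that the carried value is a 25% worsening. Shift in the arm mean per subject = (off-drug improvement + 25)/40.

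| Assumed off-drug change from Baseline | Shift in arm mean | Shift / 8.94 |
|---|---|---|
| 50% worse | (−50 + 25)/40 = −0.6 | −0.07 |
| 25% worse | (−25 + 25)/40 = 0 | 0 |
| no change | (0 + 25)/40 = 0.6 | 0.07 |
| 35% better | (35 + 25)/40 = 1.5 | 0.17 |
| 70% better | (70 + 25)/40 = 2.4 | 0.27 |

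The off-drug values are assumptions; the documents give none.

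**The case against.** **The SAP elaborates the protocol (SAP 3.0), so silence need not mean repeal.** This is fair, and it is why the point is that the rules are not carried over, not that they were deliberately removed. But 10.1.5 restates NRI in full without the stop rule, and it keeps only the rescue half of the protocol sentence that covered both groups. A programmer following it would not apply either rule.

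**Using all observed data is a legitimate treatment-policy choice.** It is. The documents do not decide between the two approaches. The fault is that the change is undeclared.

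**Few subjects may be affected.** This stands in part. An EASI 75 response after a worsening stop needs a fall from 1.25 to 0.25 of Baseline, which is 1 − 0.25/1.25 = 80% from the stopping value. The categorical half of rule (a) should therefore matter little for EASI 75. The amount of post-stop data is also unclear: Protocol 5.4.1 lists the worsening criterion among reasons for immediate withdrawal from the study, while Protocol 5.1, a later part of 5.4.1 and SAP 4.2 keep such subjects in follow-up.

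**Stronger readings that a reader might infer.**
- *Power falls below plan.* The documents give no stop or retention rates and do not say under which handling the planning means hold, so this is not supported.
- *The per-subject shifts are minimum values.* They hold only if the carried value is a 25% worsening. The protocol's point of rescue is undefined for a Period 1 stop, so another pre-imputation value might be carried.
- *Period 2 is affected as widely as Period 1.* The mandatory efficacy stop there follows topical rescue, and the SAP already excludes post-rescue data. Only stops without prior rescue are affected.

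**Conclusion.** The discrepancy is real and should be fixed. SAP 10.1.5 omits both protocol rules, and SAP 12.1 does not say so. The consequence is that the two documents can use different values in the primary endpoint after Period 1 worsening stops, and in the NRI-based EASI 75 and IGA 0/1 comparisons after any Period 1 stop. A missing Week 16 value does not remove the difference for the primary endpoint if an off-drug Week 12 value exists.

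The size is unknown. The per-subject figures above are illustrations that rest on the assumed off-drug change and on a carried value of 25% worsening, and the sign reverses if disease worsens further off drug. The primary MCP-Mod test is probably little affected. The case for action rests on unclear pre-specification, not on demonstrated bias or lost power.

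**What to change.** Before the Period 1 lock, choose one of two routes.

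1. **State the protocol's rules in SAP 10.1.5.** Extend the closing rescue exclusion to Period 1 EASI-worsening stops (NRI for categorical, LOCF for continuous, removed from OC). Define the anchor date, for example the triggering visit or the last-dose date. Reinstate, for both periods, the sentence making study-drug discontinuation a non-response under NRI. Report the all-observed-data result as a sensitivity analysis.
2. **Declare the change.** List and justify a treatment-policy analysis in SAP 12.1, and report the protocol's handling as the sensitivity analysis.

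Under either route, Protocol 5.4.1 must be reconciled with Protocol 5.1 and SAP 4.2 on whether subjects who meet the Period 1 worsening criterion stay in follow-up.

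Cost: a few lines of SAP text and one date flag in programming. No new data are needed.

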4.0 Study Objective

To evaluate the safety and efficacy of multiple doses of ABT-494 (upadacitinib) monotherapy versus placebo in the treatment of adults with moderate to severe AD.

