5.2.3.3 Prohibited Therapy

Non-Biologic Systemic Therapies

JAK Inhibitors

Prior and concomitant oral and topical exposure to any other JAK inhibitors besides the investigational drug, ABT-494 (including but not limited to ruxolitinib, tofacitinib, baricitinib, and filgotinib) is not allowed.

Other Non-Biologic Systemic Therapy

Systemic therapy for the treatment of AD is not allowed during the study, including but not limited to:

- methotrexate,
- cyclosporine,
- azathioprine,
- PDE4-Inhibitors,
- mycophenolate mofetil.

Corticosteroids

Oral, parenteral, and intralesional corticosteroids are NOT allowed during the study.

Biologic Therapies

All prior and concomitant targeted biologic therapies are prohibited during the study. Examples of targeted biologic therapies include but are not limited to the following:

- Zolair (omalizumab);
- Dupilumab;
- Adalimumab;
- Etanercept;
- Infliximab;
- Abatacept;
- Anakinra;
- Rituximab;
- Natalizumab;
- Efalizumab;
- Tocilizumab;
- Golimumab;
- Certolizumab;
- Ustekinumab;
- Belimumab;
- Secukinumab;
- Denosumab

Phototherapy, Tanning Booth, and Extended Sun Exposure

UVB or UVA phototherapy including PUVA for at least 4 weeks prior to the Baseline visit and during the study.

Tanning booth use or extended sun exposure that could affect disease severity or interfere with disease assessments for at least 4 weeks prior to the Baseline visit and during the study.

Topical Therapy

No topical treatments for AD, including but not limited to calcineurin inhibitors, corticosteroids, prescription moisturizers or moisturizers containing additives such as ceramide, hyaluronic acid, urea, or filaggrin, should be started during the course of the study; except for rescue treatment allowed in Period 2 (see Section 5.2.3.4).

Investigational Drugs

Subjects who have been treated with any investigational drug within 30 days or five half-lives of the drug (whichever is longer) prior to the first dose of study drug are excluded from participation in this study. Investigational drugs are also prohibited during the study.

Vaccines

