- In Period 2, discontinuation from study drug will be mandatory for subjects with < EASI 50 response compared with their Baseline EASI score 4 weeks following rescue with topical corticosteroids or at any visit thereafter.

Discontinuation of Study Drug and Continuation of Study Participation

In order to minimize missing data for efficacy and safety assessments, subjects who prematurely discontinue study drug treatment complete a Premature Discontinuation Visit (PD visit) as soon as possible, preferably within 2 weeks. Afterwards, subjects should continue to be followed for all regularly scheduled visits as outlined in [Table 2](#) on standard of care, unless they have decided to discontinue the study participation entirely (withdrawal of informed consent). Subjects should be advised on the continued scientific importance of their data even if they discontinue treatment with study drug early. Subjects that choose to participate in the study after discontinuation of study drug treatment should follow the regular visit schedule as outlined in [Table 2](#); and adhere to all study procedures except for dispensing study drug, PK and exploratory research sample collection. In addition, all future rescue and efficacy-driven discontinuation criteria no longer apply.

Premature Discontinuation of Study (Withdrawal of Informed Consent)

If a subject prematurely discontinues study participation (withdrawal of informed consent), the procedures outlined for the PD Visit should be completed as soon as possible, preferably within 2 weeks of the last dose of study drug, and preferably prior to the initiation of another therapy. In addition, if subject is willing, a 30-day follow-up on-site visit (or phone call if a visit is not possible) after the last dose of study drug may be completed to determine the status of any ongoing AEs/SAEs, the occurrence of any new AEs/SAEs, and medications used to treat AEs/SAEs.

All attempts must be made to determine the date of the last study drug dose and the primary reason for discontinuation of study drug or study participation. The information will be recorded on the appropriate eCRF page. However, these procedures should not interfere with the initiation of any new treatments or therapeutic modalities that the Investigator feels are necessary to treat the subject's condition. Following discontinuation of the study drug, the subject will be treated in accordance with the Investigator's best clinical judgment.

Follow-Up Period

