#### **7.4 Protocol Deviations**

Number and percentage of subjects who reported at least one of the following protocol deviation categories will be provided.

- Subject entered into the study even though she/he did not satisfy entry criteria
- Subject who developed withdrawal criteria during the study and was not withdrawn
- Subject who received wrong treatment or incorrect dose
- Subject who received excluded or prohibited concomitant treatment

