### **10.3 Primary Efficacy Analysis**

The primary efficacy variable is the percent (%) change from Baseline in EASI score at Week 16. The analysis of the primary efficacy variable will be carried out in ITT\_1 with the LOCF missing data imputation. The dose-response relationship will be evaluated by MCP-Mod method.

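### SAP 10.1.5 has no Period 1 rule for EASI scores taken after other AD therapy, and it drops two Protocol 8.1.5 rules without listing the change, so such scores enter the primary analysis as observed

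*SAP*

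**What the plan says.** **Objective.** Protocol 4.0 compares upadacitinib "monotherapy versus placebo in the treatment of adults with moderate to severe AD".

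**Primary analysis.** SAP 10.3: "The primary efficacy variable is the percent (%) change from Baseline in EASI score at Week 16", analysed in ITT_1 by MCP-Mod "with the LOCF missing data imputation".

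**Missing-data rules.** Under SAP 10.1.5, LOCF will "carry forward the most recent previous non-missing value" to fill later gaps. NRI is triggered by the absence of an evaluation in the visit window, and MI fills missing values. None of them acts on a score that was collected. The one exclusion is that "subjects who take rescue upadacitinib 30 mg or take rescue topical treatment in Period 2 will have their efficacy assessments" after the first rescue dose removed.

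**How other AD therapy can arise in Period 1.**
- Subjects who stop study drug are followed at all scheduled visits "on standard of care, unless they have decided to discontinue the study participation entirely" (Protocol 5.4.1).
- Protocol 5.2.3.3 bars starting other AD therapy: "No topical treatments for AD, including but not limited to calcineurin inhibitors, corticosteroids" and others, apart from Period 2 rescue. Under Protocol 5.4.1, taking a prohibited medication leads to withdrawal only where continuing study drug would put the subject at risk. SAP 7.4 merely tabulates it: "Subject who received excluded or prohibited concomitant treatment".

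**What Protocol 8.1.5 adds.** Subjects who stop study drug in Period 1 for EASI worsening are imputed from that point, by NRI for categorical and LOCF for continuous variables. Under NRI, anyone who stops study drug is a non-responder from the stop date. SAP 10.1.5 contains neither rule, and SAP 12.1 does not list their removal.

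**The concern.** The protocol anticipates scores at Week 16 from subjects no longer on study drug and possibly on other AD treatment. For the primary endpoint, the SAP takes those scores at face value. If other therapy is used more often where control is poorest, which is plausible for placebo, it lifts the placebo mean most. Differences from placebo then shrink, and the estimated MED, which SAP 10.1.4 ties to a 20-point difference from placebo, shifts upward. Estimating the MED is a stated purpose of the sample size.

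There is also a plain conflict between the documents. A subject who stops for EASI worsening, goes onto standard of care and attends Week 16 has the last score before the stop carried forward under the protocol, but the observed Week 16 score used under the SAP. A subject who stops for any reason and meets EASI 75 at Week 16 is a non-responder under the protocol's NRI and a responder under the SAP's.

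The SAP offers no fallback. It defines only ITT and Safety populations, although Protocol 8.1.1 left the criteria for a Per-protocol Population to it. The as-observed and MI analyses use the same collected scores.

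**Working it through.** **1. Which rule reaches which score (Period 1, a Week 16 EASI was collected)**

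| Situation | Protocol 8.1.5 | SAP 10.1.5 |
|---|---|---|
| Stopped for EASI worsening, continuous EASI | LOCF from the stop | used as observed |
| Stopped for EASI worsening, binary | non-responder | used as observed |
| Stopped for another reason, then standard of care, continuous EASI | no rule | used as observed |
| Stopped for another reason, binary (NRI) | non-responder | used as observed |
| Prohibited AD therapy while on study drug, any endpoint | no rule | used as observed |

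**2. The plan's own power figures**

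Inputs (Protocol 8.2, SAP 4.3): mean improvements 35, 45, 60 and 70 for placebo, 7.5, 15 and 30 mg; SD 40; 40 per arm. Differences from placebo: 10, 25 and 35. The standard error of a difference is 40 × √(2/40) = 8.94.

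- Two-sample t-test, two-sided 5%: 97.2% for 30 mg (stated 97%) and 78.8% for 15 mg (stated 78%).
- MCP step, simulated with optimal contrasts for the six shapes in SAP Table 13 at one-sided 5%: 99.3% at the planned means (the plan states 99% average power).

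The plan's figures reproduce.

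**3. Effect of leaving the scores in**

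The documents give neither usage rates nor gains. Assumptions: a share p_P of 10–30% on placebo and p_A of 5–10% on each active arm have a Week 16 score on other AD therapy; each such score improves by g = 20–40 points; the SD stays at 40; the active share is the same at every dose.

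Loss in each difference from placebo = (p_P − p_A) × g.

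- Smallest: (0.10 − 0.10) × g = 0.
- Middle: (0.20 − 0.10) × 30 = 3.
- Largest: (0.30 − 0.05) × 40 = 10.

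MED by straight-line interpolation of the reduced differences to 20 points:

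- Loss 0: 7.5 + 7.5 × (20 − 10)/15 = 12.5 mg.
- Loss 3: 7.5 + 7.5 × (20 − 7)/15 = 14.0 mg.
- Loss 10: 15 + 15 × (20 − 15)/10 = 22.5 mg.

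| Loss (points) | 15 mg difference | Interpolated MED | Power, 15 mg vs placebo (t-test) | Power, MCP step |
|---|---|---|---|---|
| 0 | 25 | 12.5 mg | 79% | 99.3% |
| 1 | 24 | 13.0 mg | 75% | 99.1% |
| 3 | 22 | 14.0 mg | 68% | 98.5% |
| 8 | 17 | 19.5 mg | 47% | about 95% |
| 10 | 15 | 22.5 mg | 38% | about 93% |

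The interpolated MED shows direction and rough size only. SAP 10.1.4 takes an AIC-weighted average over the fitted significant models, which this does not reproduce.

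**The case against.** **Using all collected data is a recognised ITT choice.** Protocol 5.4.1 keeps off-drug subjects in follow-up expressly to limit missing data, SAP 5.1 analyses subjects as randomised, and the objective in SAP 4.1 omits the word monotherapy. This stands in part: the strategy would be defensible if stated. It is not stated, and both documents depart from it elsewhere (Protocol 8.1.5 for Period 1 stops, SAP 10.1.5 for Period 2 rescue).

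**A reader might infer that the SAP excludes in Period 2 exactly what it counts in Period 1.** The documents do not support that. The Period 2 exclusion covers only the two protocol rescues, which do not exist in Period 1. Prohibited therapy, and standard of care after a study-drug stop, are unaddressed in Period 2 as well.

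**A reader might infer that the protocol covers only stops for EASI worsening.** It does not: its NRI rule covers every study-drug stop. For binary endpoints after a stop, the fault is therefore an unlisted SAP departure. For the continuous primary endpoint, the gap exists in both documents, except for stops due to worsening.

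**The affected group may be small.** Protocol 5.4.1 lets investigators withdraw non-responders from the trial, and those subjects may have no Week 16 score. This is fair; the size is unknown.

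**Excluding the scores has costs.** Collected values are replaced by imputed ones. Off-drug scores without other therapy can also remain in the continuous analysis, so the result is not a pure on-treatment effect. Both points stand, and they are a reason to report the two analyses side by side.

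**Conclusion.** The point holds. Under the SAP, a Period 1 Week 16 EASI taken after standard of care or prohibited AD therapy counts as the effect of the randomised arm. That does not match the monotherapy objective, and two protocol rules have gone without being listed. If such use is commoner on placebo, the bias is toward smaller differences and a higher MED.

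The size rests wholly on assumed rates and gains. Over the range used, the loss is 0–10 points, so no effect at all is within the range. The reading that the primary test is badly underpowered is not supported: MCP-step power stays at about 93% in the worst case. The fall from 79% to 38% belongs to the pairwise comparison of 15 mg with placebo. The MED is the more exposed quantity. The change is worth making because it is cheap and the SAP and protocol have to be reconciled in any case.

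**What to change.** In an SAP amendment before database lock and blind break:

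1. Restore the two Protocol 8.1.5 Period 1 rules in SAP 10.1.5, or list and justify their removal in 12.1.
2. Exclude Period 1 efficacy assessments after the first use of any AD therapy prohibited in Protocol 5.2.3.3, on or off study drug. Handle them by NRI for binary endpoints, and by LOCF with MI as sensitivity for continuous endpoints, including the MCP-Mod input.
3. Report the analysis of all collected data alongside, and say which question each analysis answers.

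Take start dates from the medication eCRF required by Protocol 5.2.3. The definition of concomitant medication in SAP 7.3 stops at the last dose of study drug, so it would miss standard of care begun afterwards.

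Cost: a few paragraphs of SAP text and one extra run, with no change in trial conduct. A few collected values become imputed ones. A subject with no post-baseline score before the other therapy drops out of the LOCF analysis, because baseline is not carried forward; the MI analysis covers that case.
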